### **3.8.2.5 Time to Next Therapy (TTNT)**

The TTNT will be measured as the time from first treatment to the time of new systemic cGVHD treatment, censored by last response assessment or long term follow up assessment, whichever is the latest and available. TTNT will be analyzed by the Kaplan-Meier survival method as well as the landmark analysis at 6, 12, 18, and 24 months.

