11.7.2 Secondary Efficacy Endpoints

Secondary endpoints are as follows:

- Duration of response (DOR): Assessments of DOR will include:
 - The time from initial response of PR or CR until documented progression from best response of cGVHD, new cGVHD therapy, or death.
 - Time from initial response to start of additional systemic cGVHD therapy or death.
- Changes in the Lee Symptom Scale Score: Analyses will include:
 - Number of participants with a ≥ 7 point reduction.
 - Number of participants with a ≥ 7 point reduction on 2 consecutive assessments.
 - Duration of a ≥ 7 point reduction.
- Response by organ system: The response assessment for the nine individual organs (Skin, Eyes, Mouth, Esophagus, Upper GI, Lower GI, Liver, Lungs, and Joints and fascia).
- Time to response (TTR): defined as the time from the first dose of belumosudil to the first documented cGVHD response.
- Time to next therapy (TTNT): defined as the time from the first dose of belumosudil to the start of additional systemic cGVHD therapy.
- Number and percentage of participants who have a best response of PR and number and percentage of participants who have a best response of CR.
- Change in corticosteroid dose:
 - The prednisone equivalent dose of corticosteroids (mg/kg/day) during the study will be analyzed ([Appendix K](#)).
- Change in calcineurin inhibitor dose.
- Failure-free-survival (FFS): FFS is defined as the absence of cGVHD treatment change, non-relapse mortality and recurrent malignancy ([Section 6.3.5](#)). Median FFS (from first dose of belumosudil) and landmark FFS at 1 year will be analyzed.
- Overall survival (OS): Defined as time from first dose of belumosudil to the date of death due to any cause.
- Changes in cGVHD global severity rating using the Clinician-Reported Global cGVHD Activity Assessment.

- Changes in symptom activity using the cGVHD Activity Assessment Patient Self-Report.

Descriptive statistics will be provided for all secondary endpoints.

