### **3.8.2.8 Failure-free-survival (FFS)**

FFS is defined as the absence of new cGVHD systemic therapy, non-relapse mortality and recurrent malignancy (i.e. underlying disease) and is censored by last response assessment or long term follow up assessment, whichever is the latest and available. Kaplan-Meier plots, descriptive statistics of FFS and landmark FFS at 6, 12, 18 and 24 months will be provided. In addition, analyses for the three components of FFS will also be provided.

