T	Descriptive statistics for prednisone equivalent dose of corticosteroids for a) change and % change from baseline to greatest reduction; b) the number and % subjects who reduced dose; c) number and % subjects who discontinued corticosteroid usage	miITT, Responder, Nonresponder, BL corticosteroid dose level (upper and lower 50 th percentiles)

T/L/F	Title	Population
T	Descriptive Kaplan-Meier statistics for time to corticosteroid discontinuation	miITT
T	Summary of raw and change from baseline on prednisone equivalent dose of corticosteroids by visit	miITT, Responder, Nonresponder, BL corticosteroid dose level (upper and lower 50 th percentiles)
F	Box plot of prednisone equivalent dose of corticosteroids over time	miITT, Responder, Nonresponder, BL corticosteroid dose level (upper and lower 50 th percentiles)
L	Listing of all the steroid raw and standardized dosing by subject and visit	miITT
Secondary Endpoint: CNI Dose		
T	Summary of descriptive statistics for CNI for a) the number and % subjects who reduced dose from baseline; b) number and % subjects who discontinued CNI	miITT
L	Listing of all the CNI dosing by subject and visit	miITT
Secondary Endpoint: FFS		
T	Descriptive Kaplan-Meier and landmark (6, 12, 18 and 24 months) statistics for FFS (with cumulative failure rates for each of the 3 components FFS)	miITT
F	Kaplan-Meier plot for FFS (with cumulative failure rates for 3 components of failures)	miITT
L	Listing of failure events	miITT
Secondary Endpoint: OS		
T	Descriptive Kaplan-Meier and landmark (6, 12, 18 and 24 months) statistics for OS	miITT
F	Kaplan-Meier plot of OS	miITT
Secondary Endpoint: Symptom activity using the cGVHD Activity Assessment Patient Self-Report		
T	Descriptive statistics of change from baseline in symptom activity based on cGVHD Activity Assessment Patient Self Report (global rating) by visit	miITT

T/L/F	Title	Population
T	Descriptive statistics of symptom activity based on cGVHD Activity Assessment Patient Self Report (change of cGVHD symptom to a month ago) by visit	miITT
L	Listing of symptom activity based on cGVHD Activity Assessment Patient Self Report	miITT
Exploratory Endpoints		
T	Overall Response Rate (KARA)	miITT
T	Concordance of overall response between investigator determined responses and KARA	miITT
T	Descriptive Kaplan-Meier and landmark (12, 20, 24, 32, 36, 48 weeks) statistics for DOR (KARA)	Responder

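### TTNT is analysed by Kaplan-Meier with death and malignancy recurrence acting as censoring, so 1−KM overstates the share of participants who start new cGVHD therapy

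*SAP*

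**What the plan says.** SAP 3.8.2.5 defines the endpoint by one event: "The TTNT will be measured as the time from first treatment to the time of new systemic cGVHD treatment". All other participants are "censored by last response assessment or long term follow up assessment, whichever is the latest and available". The method is stated as "TTNT will be analyzed by the Kaplan-Meier survival method", with a landmark analysis listed beside it at 6, 12, 18 and 24 months. Protocol 11.7.2 has the same single event: TTNT is "defined as the time from the first dose of belumosudil to the start of additional systemic cGVHD therapy". Neither text mentions death or recurrence of the underlying malignancy.

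Both appear in a neighbouring endpoint. SAP 3.8.2.8 states that "FFS is defined as the absence of new cGVHD systemic therapy, non-relapse mortality and recurrent malignancy", to be analysed by Kaplan-Meier at the same four landmarks, and adds that "analyses for the three components of FFS will also be provided". The output list in SAP Appendix A (Table 4) describes the FFS table and figure, the table "with cumulative failure rates for each of the 3 components FFS". Neither place says how those component rates are estimated.

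Protocol 6.2.8 has participants contacted about every 12 weeks, but only until an FFS event or study close-out.

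**The concern.** A participant who dies without new therapy can no longer start it. Censoring that participant removes them from the risk set and lets those still under observation stand in for them, as though the dead would have gone on to new therapy at the same rate. If deaths are independent of the need for therapy, 1−KM estimates a hypothetical probability in a world without death. It does not estimate the proportion of treated participants who start another systemic therapy, which is how an 18- or 24-month TTNT figure is likely to be read.

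Recurrence has a similar effect for a different reason. It is an FFS event, so contact stops, and any new cGVHD therapy started later is not sought.

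The SAP does not treat death this way throughout. In its censoring table for duration of response (Table 3, section 3.8.2.1), the tertiary definition counts death as an event beside new systemic therapy. That endpoint differs from TTNT mainly in its starting point and in being restricted to responders. No reason is given for the different handling.

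At stake is the meaning of the TTNT landmarks, and whether they can be reconciled with the new-therapy component of FFS.

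**Working it through.** **Plan's own figure.** There is none. The documents state no rate for new therapy, death or recurrence, and no TTNT power. Every rate below is an assumption.

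**Formulas.** Let *a* be the hazard of new therapy and *b* the hazard of death without it, constant and independent, with *t* in years.

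- Kaplan-Meier with deaths censored: 1−KM = 1 − exp(−*a t*)
- Cumulative incidence (what Aalen-Johansen estimates): *a*/(*a*+*b*) × [1 − exp(−(*a*+*b*)*t*)]

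**Example.** For *a* = 0.6, *b* = 0.15, *t* = 2: 1−KM = 1 − exp(−1.2) = 69.9%. Cumulative incidence = 0.8 × [1 − exp(−1.5)] = 62.1%. The excess is 7.7 points before rounding.

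**All four corners of the assumed range** (excess taken before rounding):

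| *a* | *b* | 12 mo: 1−KM | 12 mo: cum. inc. | Excess | 24 mo: 1−KM | 24 mo: cum. inc. | Excess |
|---|---|---|---|---|---|---|---|
| 0.4 | 0.08 | 33.0% | 31.8% | 1.2 | 55.1% | 51.4% | 3.6 |
| 0.4 | 0.15 | 33.0% | 30.8% | 2.2 | 55.1% | 48.5% | 6.5 |
| 0.6 | 0.08 | 45.1% | 43.5% | 1.6 | 69.9% | 65.6% | 4.3 |
| 0.6 | 0.15 | 45.1% | 42.2% | 2.9 | 69.9% | 62.1% | 7.7 |

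**Wider range.** With one-year probabilities of 20 to 50% for new therapy and 5 to 20% for death, the excess is 0.1 to 1.5 points at 6 months, 0.5 to 4.6 at 12 months and 1.7 to 11.5 at 24 months.

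**Finite samples.** Both estimators were applied to 2,000 simulated samples of 126 participants per scenario, with 35% new therapy and 5, 10 or 15% death at one year. The mean excess was 0.8, 1.7 and 2.6 points at 12 months and 2.5, 4.9 and 7.4 points at 24 months. No sample gave a negative excess.

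**Consistency with FFS.** Assume one-year probabilities of 35% for new therapy, 10% for non-relapse death and 5% for recurrence. The yearly hazards are −ln 0.65 = 0.431, −ln 0.90 = 0.105 and −ln 0.95 = 0.051, which sum to 0.587. At 24 months, 1−FFS = 1 − (0.65 × 0.90 × 0.95)² = 69.1%.

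| Component estimator | New therapy | Non-relapse death | Recurrence | Sum | 1−FFS |
|---|---|---|---|---|---|
| Cumulative incidence | 50.7% | 12.4% | 6.0% | 69.1% | 69.1% |
| 1−KM for each | 57.7% | 19.0% | 9.8% | 86.5% | 69.1% |

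In the first row the components sum to total failure, but TTNT by 1−KM (57.7%) lies about 7 points above the new-therapy component. In the second row TTNT matches its component, but the three sum to 86.5%, which is 17.4 points above total failure.

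**Why recurrence must be included.** With death alone competing, the cumulative incidence of new therapy at 24 months in this example is 52.9%. With recurrence competing as well it is 50.7%. Correcting for death only would leave TTNT about 2 points above the FFS component.

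**The case against.** The case for leaving the plan alone has real parts.

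- **TTNT is descriptive.** SAP section 3 allocates alpha only to ORR, and section 3.2 makes all secondary endpoints descriptive. This stands and limits the consequence.
- **The bias is conservative.** It makes new therapy look more frequent than it is, which works against belumosudil. A reader might infer that the method flatters the drug; it does the opposite.
- **Sampling error is larger.** For a proportion near 40% without censoring, the 95% half-width is 1.96 × √(0.4 × 0.6/126) ≈ 9 points overall and 1.96 × √(0.4 × 0.6/63) ≈ 12 points per arm. That is well above the 12-month excess. The excess, however, does not shrink as the sample grows.
- **Death is visible elsewhere.** FFS and OS are reported at the same landmarks. This helps a careful reader but does not correct the TTNT figure.
- **The single-event definition follows the protocol.** It does, but the definition does not require Kaplan-Meier with deaths censored.

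Two stronger readings are tempting and go beyond the text. A reader might infer that TTNT is bound to disagree with the FFS component rates. The SAP names no component estimator, so it may or may not. A reader might also infer that the landmark figures are certainly biased. The SAP lists the landmark analysis alongside Kaplan-Meier without saying that it is read from the curve, and for duration of response its landmark analyses are counts and percentages. The landmark bias is therefore conditional.

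**Conclusion.** The point holds as a minor one. Kaplan-Meier is specified with a single event. Censoring of deaths is implied by the rule rather than stated, and recurrence acts as censoring through the end of long-term contact. As an estimate of the share of participants who start new systemic therapy, 1−KM is too high. The direction needs no assumption about rates: 1−KM is never below the cumulative incidence, and exceeds it once a death precedes a later new-therapy event. The size, about 1 to 3 points at 12 months and 4 to 8 at 24 months, rests on assumed constant, independent hazards of 0.4 to 0.6 and 0.08 to 0.15 per year, with death as the only competing event. Adding recurrence widens the gap.

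On FFS, the documents support only an either-or statement. If the component rates are cumulative incidences, TTNT by 1−KM will exceed the new-therapy component. If each is 1−KM, the three will not sum to 1−FFS. The ORR decision is unaffected.

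**What to change.** In SAP 3.8.2.5:

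- Report the Aalen-Johansen cumulative incidence of next systemic cGVHD therapy at 6, 12, 18 and 24 months, and state that the landmarks come from this curve.
- Name death without next therapy and malignancy recurrence before next therapy as competing events, each dated at its occurrence rather than at the preceding assessment.
- Keep Kaplan-Meier as a supplement, with a note that it censors these events.

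In SAP 3.8.2.8 and the Appendix A output list, name the same estimator for the three FFS components, so that they sum to 1−FFS and the new-therapy component matches TTNT. Add a TTNT entry to Table 4 of Appendix A, which currently lists none.

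The cost is a few lines of SAP text and a standard procedure. New therapy, death and recurrence are already needed for FFS, so no further data collection is required. The downside is a summary slightly less familiar than a Kaplan-Meier median. Because recurrence, unlike death, does not make later cGVHD therapy impossible, the text should say that the quantity reported is next therapy before recurrence.

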### **3.8.2.6 Corticosteroid dose**

Corticosteroid doses will be presented as mg/kg/day prednisone equivalent dose. Descriptive statistics for the mITT population, responder /nonresponder populations and subgroups defined by baseline corticosteroid dose level (upper and lower 50 percentiles) will be provided for:

- Systemic corticosteroid dose over time
- Change and % change from baseline (C1D1) to the greatest corticosteroid dose reduction during KD025 treatment period
- Number and % of subjects who reduced systemic corticosteroid dose during KD025 treatment period

- Number and % of subjects who ever discontinued systemic corticosteroid usage for over 28 days during KD025 treatment period

The above analyses will be censored on or after new systemic cGVHD treatment.

If subjects are not using prednisone as the systemic corticosteroid, then the prednisone dose equivalent will be determined according to following conversion ratios:

1 mg prednisone is equivalent to:

- 4mg Hydrocortisone
- 0.8mg Methylprednisolone
- 0.15mg Dexamethasone
- 1mg Prednisolone
- 0.8mg Triamcinolone

Transient increases in corticosteroid dosing (not exceeding 1mg/kg/day prednisone equivalent, are permitted for the treatment of cGVHD flare, but dose must be reduced back to the pre-randomization dose within 6 weeks. If the dose remains elevated for more than 6 weeks, this will be considered a KD025 treatment failure. More than 2 episodes of cGVHD flare requiring increased corticosteroid therapy in the first 6 months of KD025 treatment will also be considered a KD025 treatment failure.

### **3.8.2.7 Calcineurin inhibitor (CNI) doses**

CNI includes systemic tacrolimus and cyclosporine. Descriptive statistics will be provided for:

- Number and % of subjects who reduced CNI dose during KD025 treatment period
- Number and % of subjects who ever discontinued CNI during KD025 treatment period

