### 3.4 Analysis Populations

**mITT:** The primary population for efficacy analyses will be a modified Intent to treat (mITT) population defined as all randomized subjects who receive at least one dose of study medication.

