#### **Reporting of Numerical Values**

Continuous data will be described using descriptive statistics: number of observations (n), mean, standard deviation, median, minimum and maximum. Frequencies and percentages will be used for summarizing categorical data. When categorical data are presented, the percent will be suppressed when the count is zero in order to draw attention to the nonzero counts. The denominator for all percentages, unless otherwise specified, will be the number of subjects in the specified analysis population or group.

Means, medians, standard deviations, and confidence intervals will be reported to one decimal place more than the data reported on the case report form (CRF) or by the laboratory/vendor. Minimum and maximum will be reported to the same number of decimal places displayed on the CRF or by the laboratory/vendor. P-values will be reported to 4 decimal places.

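### The percentages reducing or stopping a calcineurin inhibitor are taken over all mITT participants, so they mix the rate among users with the share who used the drug at entry

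*SAP*

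**What the plan says.** SAP 3.8.2.7 lists two CNI summaries: "Number and % of subjects who reduced CNI dose during KD025 treatment period" and "Number and % of subjects who ever discontinued CNI during KD025 treatment period". It names neither a denominator nor a population.

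Three other places fill the gap:

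- SAP 3.14, Reporting of Numerical Values: "The denominator for all percentages, unless otherwise specified, will be the number of subjects in the specified analysis population or group".
- SAP Appendix A, Table 4, describes the CNI output as "Summary of descriptive statistics for CNI for a) the number and % subjects who reduced dose from baseline", with discontinuation as part b. Its population column says mITT only.
- SAP 3.4 defines mITT as "all randomized subjects who receive at least one dose of study medication". Background treatment at baseline plays no part in the definition.

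Protocol 4.3, inclusion criterion 3, lists corticosteroids and CNIs among the acceptable concomitant treatments. It does not require either.

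For steroids, SAP 3.8.2.6 asks for "Number and % of subjects who reduced systemic corticosteroid dose during KD025 treatment period" and for the number and percentage discontinuing. Its populations are wider: "Descriptive statistics for the mITT population, responder /nonresponder populations and subgroups defined by baseline corticosteroid dose level". It too does not limit these percentages to baseline users.

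By contrast, SAP 3.8.2.3 handles the same structural problem for organ response. There, one stated denominator is the mITT participants who had that organ involved at baseline.

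**The concern.** Someone who takes no CNI at C1D1 has no dose to reduce or stop. Protocol 3.1 does not permit starting a new systemic cGVHD therapy on study, and Protocol 5.8 treats doing so as treatment failure that ends study drug. While the protocol is followed, a baseline non-user cannot enter the CNI numerator during the treatment period but stays in the denominator.

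The endpoint is meant to describe CNI-sparing, and it is a named secondary endpoint. Under the default rule, the printed percentage partly describes how many participants happened to be on a CNI at entry. Two arms with the same effect among users would show different percentages if their baseline use differed. SAP 2.4 stratifies on prior ibrutinib and severe cGVHD, not on background CNI, so chance differences in use are possible.

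**Working it through.** The documents state no baseline usage share and no expected reduction rate, so there is no planned figure to reproduce. The check has two parts.

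**Which denominator applies**

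1. SAP 3.8.2.7 specifies none.
2. SAP 3.14 therefore sets it to the specified analysis population.
3. Appendix A, Table 4 specifies mITT.
4. mITT has no baseline-use condition, and Protocol 4.3 does not require CNI use. No other section restricts the percentage to users.

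**What that does to the rate**

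Let f be the share of mITT on a CNI at C1D1 and r the proportion of those users who reduce. With no non-users in the numerator:

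reported rate = (users who reduce) / (all mITT) = f × r.

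Inputs: 63 per arm comes from the SAP's sample size (3.1). The values of f and r = 40% are assumptions. Counts are rounded to whole participants, and intervals are Clopper-Pearson 95%.

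| Assumed f | Users of 63 | Reduce | Among users | Over mITT |
|---|---|---|---|---|
| 20% | 13 | 5 | 5/13 = 38.5% | 5/63 = 7.9% |
| 40% | 25 | 10 | 10/25 = 40.0% (21.1 to 61.3) | 10/63 = 15.9% (7.9 to 27.3) |
| 60% | 38 | 15 | 15/38 = 39.5% | 15/63 = 23.8% |
| 80% | 50 | 20 | 20/50 = 40.0% (26.4 to 54.8) | 20/63 = 31.7% (20.6 to 44.7) |
| 95% | 60 | 24 | 24/60 = 40.0% | 24/63 = 38.1% |

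At f = 100% there is no dilution.

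**Arm comparison (assumed imbalance)**

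Take 30% use in one arm (19 of 63) and 45% in the other (28 of 63), with about 40% of users reducing in each:

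- First arm: 8/19 = 42.1% among users; 8/63 = 12.7% over mITT.
- Second arm: 11/28 = 39.3% among users; 11/63 = 17.5% over mITT.

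The user rates are nearly equal and differ only through rounding to whole participants. The mITT percentages differ by 17.5 − 12.7 = 4.8 points, in the opposite direction.

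**The case against.** **The text is ambiguous.** The mITT reading joins a default rule to a population column; 3.8.2.7 itself is silent. The Table 4 wording refers to reduction from baseline, which presupposes a baseline dose. SAP 3.14 also says that a participant without pre-dose data on a parameter has a missing baseline, and that missing data drop out of percentages. A non-user might be excluded that way. This is arguable, but not taking a drug is a known state rather than missing data, and a non-user could equally be coded as dose 0. Nothing in the SAP displaces the default.

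**The user-based rate can be rebuilt.** SAP 3.7.3 summarizes systemic cGVHD therapies ongoing at baseline, counts accompany percentages, and CNI dosing is listed by subject and visit. That stands, so it would be too strong to say that the arms cannot be compared. It does not correct the percentage the table will print.

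**Steroids.** A reader might infer that the steroid percentages are diluted just as badly, because criterion 3 as amended in Amendment 5 accommodates entry without steroids. The documents do not support that:

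- SAP version 2.1 follows a version written for Amendment 1 and covers about 126 randomized participants.
- Amendment 5 came after Amendment 4 of April 2022. Adolescents enrolled since Amendment 4 are not randomized (Protocol 3.1), so they fall outside mITT as defined.
- Protocol 1.5 still describes disease active despite corticosteroid treatment.

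Nor is it strictly true that a steroid non-user can never enter the numerator, since Protocol 5.8.1 permits transient steroid increases for flare.

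**Low stakes.** SAP 3.2 makes all secondary endpoints descriptive, without multiplicity adjustment, and dilution lowers the reported rate rather than flattering it. This limits the consequence but does not remove it.

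**Conclusion.** The point holds for the CNI percentages. Followed as written, the SAP reports f × r where r is the quantity of interest. The size cannot be fixed from the documents: at an assumed r of 40% and 63 per arm, the report would read 15.9% at 40% baseline use and 31.7% at 80%, and dilution becomes negligible as use approaches 100%. Descriptive arm comparisons are exposed to chance differences in baseline use.

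The same default applies to the steroid reduction and discontinuation percentages, but the effect is probably small in the cohort this SAP covers. Amendment 5's criterion 3 is not evidence for it.

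A reader might also infer a threat to the trial's error control. There is none: alpha is allocated only to ORR (SAP 3), so neither type I error nor power is touched. What suffers is the interpretation of a secondary endpoint.

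**What to change.** In SAP 3.8.2.7 and its Table 4 entry, and for consistency in 3.8.2.6:

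- Set the denominator for reduction and discontinuation as mITT participants with a C1D1 dose of the drug above 0. This follows the approach SAP 3.8.2.3 already takes for organ response.
- Show the number of baseline users over the number in mITT, by arm.
- Count participants who first start the drug after baseline separately.
- Keep the mITT percentage, if wanted, as a labelled supplement.

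No new data are needed, because Protocol 5.8.1 and 5.8.2 already collect these doses throughout. The cost is about a sentence per endpoint, plus a smaller denominator and a wider interval. In the 40% use example, the 95% interval spans 61.3 − 21.1 = 40.2 points among users, against 27.3 − 7.9 = 19.4 points over mITT.
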